3.2 Study Outcome Measures

3.2.1 Primary

The primary end point will be to achieve >=30% reduction (Yes/no) in monthly (28 days) average pain score from baseline to Visit 4 (the last monthly treatment cycle), compared to placebo. The daily pain intensity score will be measured on a 11-point (0-10) numeric rating scale (NPRS) and reported in the Daily Symptom Diary (DSD). The monthly mean pain intensity score will be determined from baseline (4 weeks/28 days), for each month during the 12 weeks of treatment.

The monthly mean pain intensity score will be calculated if a participant has at least 80% compliance with the DSD.

A relevant decrease in chronic pain showing a beneficial effect will be a reduction of >=30% from baseline in the average pain intensity score [29, 30].

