5.5.2 Handling of Subject Withdrawals or Subject Discontinuation of Study Intervention

Participants withdrawn after randomization will not be replaced. Participants who are withdrawn voluntarily or by the investigator will be discontinued from the study.

Study staff will complete a study disposition form in the eCRF, indicating the reason for discontinuation.

If the patient is a patient from the school and/or is interested in following orofacial pain care at the Brotman Facial Pain clinic, will be referred to the faculty practice clinic front desk for information and to schedule an appointment if wants to.

Unblinding, if required, will be carried out according to the procedures described in Section 5.4.2. A participant who has an AE at the time of discontinuation will be followed until the event returns to baseline, resolves, or is stabilized. If the AE does not meet one of these outcomes within 30 days after discontinuation or the end of the study, the participant will be referred to an appropriate provider for continued medical care (See section 9.2).

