6.3 Modification of Study Product Administration for a Subject

If a dose of Erenumab is missed, will be administered as soon as possible. Thereafter, Erenumab will be scheduled monthly from the date of the last dose.

The safety profile of erenumab has been favorable in clinical trials and in the post-marketing setting. A limited number of adverse drug reactions (injection site reactions, constipation, muscle spasm, and pruritus) have been identified at low frequencies (< 5%) in clinical trials. In the long-term use of erenumab, the safety profile remained consistent through 5 years of open-label treatment. In post-marketing settings, hypersensitivity reactions (including rash, angioedema and anaphylactoid reactions) and constipation with serious complications have been reported. In addition, oral sores (eg, stomatitis, mouth

ulceration, oral mucosal blistering), alopecia and rash (eg, rash papular, exfoliative rash, rash erythematous, urticaria, blister) have been observed in post-marketing surveillance.

Adverse reactions with the use of Erenumab have been hypersensitivity reactions, constipation with serious complications and hypertension. Exclusion criteria includes medical history of constipation or taking medications associated with decrease of G.I motility as well as pre-existent hypertension (See 5.2). If the participant reports a hypersensitivity reaction (rash, angioedema, anaphylaxis), new onset constipation or new onset of hypertension or if the participant decides against using Erenumab, he/she will be discontinued from the study (See 2.3.1 and 5.5.2).

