6.6.4 Not allowed medications

Participants cannot take as rescue medication or start therapy with any oral antiepileptics, SSRIs, SSNRIs, MAOIs, tricyclics antidepressants, tizanidine, baclofen, prednisone during the study (Please see Appendix B). In addition, they cannot receive any nerve blocks, onabotulinum toxin A injections, or use prescription compound topicals (except the ones that can be used as rescue mentioned above) or drug infusions for the management of TNP.

Participants who are currently taking pain medication for TNP and the rescue medication was not helpful and are in need of other strategy due to TNP, they will need to be withdrawn from the study to follow up with TNP management (this being dosage adjustment of the medication they are currently taking for the management of TNP or other).

Participants who are not currently taking pain medication for TNP, and the rescue medication was not helpful and are in need of other strategy. They will need to be withdrawn from the study to follow up with TNP management.

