6.6.5 Nonpharmacologic Therapy

<30 March 2022>

During the course of the study, participants will not be restricted in the use of non-pharmacological therapies, excluding Cognitive Behavioral Therapy (CBT) and acupuncture. If a participant starts these for the complementary management of pain during the study, the use of these therapies will be recorded in the eCRF and the patient will need to be withdrawn of the study.

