7.3.2 Visit 2, 2nd treatment/cycle (Day 28+/-3 days/ 4 weeks after Visit 1)

- Review Daily Symptom Diaries in eCRF or collect and review it in paper forms
- Assess compliance with Daily Symptom Diaries
- Review medical history
- Record concomitant medications and therapies
- Take blood pressure and collect weight
- Assess and record adverse events (AEs)
- Perform urine pregnancy test (in women of childbearing potential)
- Review 4 questionnaires from Visit 1 in eCRF or collect and review the paper forms
- Provide instruction to complete 4 new outcome measure questionnaires in paper or electronically for review at Visit 3.
- Provide instruction to complete Daily Symptom Diaries electronically or provide them in paper forms
- Deliver the injection of the study drug or placebo
- Schedule next visit

7.3.3 Visit 3, 3rd and final treatment cycle (Day 56+/- 3 days after 4 weeks from Visit 2)

Review Daily Symptom Diaries in eCRF or collect and review it in paper forms

- Assess compliance with Daily Symptom Diaries
- Review medical history
- Record concomitant medications and therapies
- Take blood pressure and collect weight
- Assess and record adverse events (AEs)
- Perform urine pregnancy test (in women of childbearing potential)
- Review 4 questionnaires from Visit 2 in eCRF or collect and review the paper forms
- Provide instruction to complete 4 new outcome measure questionnaires in paper or electronically for review at Visit 4.
- Provide instruction to complete Daily Symptom Diaries electronically or provide them in paper forms
- Deliver the injection of the study drug or placebo
- Schedule next visit

7.3.4 Visit 4, assessment of last treatment cycle (Day 84+/- 3 days,4 weeks after Visit 3

- Review Daily Symptom Diaries in eCRF or collect and review it in paper forms
- Assess compliance with Daily Symptom Diaries
- Review medical history
- Record concomitant medications and therapies
- Take blood pressure and collect weight
- Assess and record adverse events (AEs)
- Perform QST

- Perform EEG
- Collect blood for Cytokine release assay
- Perform urine pregnancy test (in women of childbearing potential)
- Review 4 questionnaires from Visit 3 in eCRF or collect and review the paper forms
- Provide instruction to complete 4 new outcome measure questionnaires in paper or electronically for review at Visit 5.
- Provide instruction to complete Daily Symptom Diaries electronically or provide them in paper forms
- Schedule next visit

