7.5 Withdrawal Visit

An early termination visit will be performed if a participant is suspended before the completion of the study, prior to withdrawal of consent and with the participant's permission. This could happen during a scheduled or unscheduled visit. The investigator, study coordinator or research staff will discuss with the participant to contact the research team in case AE arise after the withdrawal visit. The assessment and procedures of Visit 4 will be conducted at this visit.

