Extraoral chair side QST: The cotton swab test will test sensitivity to non-painful mechanical stimulation (low-sensitivity). With the use of a cotton swab, the skin will be gently stroked 3-4 times with strokes of 1-2 cm in length in the area of V1, V2 and V3 and we will compare responses between the non-painful side to the painful side to detect normosensitivity, hyposensitivity, hypersensitivity and allodynia.

The spatula test will test temperature sensitivity following the same procedure as in the other 2 tests and temperature will be applied for 2-3 seconds. It is performed with a spatula that will be cold not exceeding 5 degrees Celsius or heated in a water bath until is 40 degrees Celsius.

EEG Assessment

EEG assessment will be performed in all participants. In chronic pain patients, alpha rhythms are slower in frequency and elevated in power relative to matched, healthy controls[39, 40]. Within the alpha band, the frequency at which maximum power is displayed, known as peak alpha frequency (PAF), varies considerably amongst individuals [45]. We have shown that PAF predicts future pain sensitivity in multiple experimental pain models [41-43]. We will examine whether erenumab can modulate PAF and therefore mediate clinical effects. PAF is based on a 5-minute, eyes-closed resting state EEG.

Daily Symptom Diary

Participants will be asked to complete the Daily Symptom Diary at the end of each day starting at the baseline phase and through the entire study (visits 1-5). Participants should have at least 80% compliance with the DSD the entire month, the equivalent of 23 completed days.

The diary collects the participant's pain intensity (reported on a 0-10 numeric rating scale) and use of pain medication. Participants are required to complete a Daily Symptom Diary electronically or on paper and a new form will be used for each month of the study. These forms may be returned in person at study visits.

Outcome Measure Questionnaires

Listed in the Schedule of Events (Appendix A). Questionnaire forms on paper will be provided to the participants if an electronic form is not feasible.

Some questionnaires are self-administered, and others will be administered by trained study staff.

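### Participants who stop the injections or need other pain treatment leave the study and its diary; removal before about Day 79 (Day 62 on the looser rule) leaves no primary score from the last diary month.

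*Combined protocol and SAP*

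**What the plan says.** **Exit rules.** Section 6.3 lists hypersensitivity reactions and continues: "new onset constipation or new onset of hypertension or if the participant decides against using Erenumab, he/she will be discontinued from the study". Section 2.3.1 repeats this for new constipation, and Section 9.3.2 for new constipation and new hypertension. Under Section 6.6.4, people whose rescue medication fails and who need another strategy are told "they will need to be withdrawn from the study to follow up with TNP management". Under Section 6.6.5, once CBT or acupuncture is started, "the patient will need to be withdrawn of the study". Section 5.5.2 closes the loop: "Participants who are withdrawn voluntarily or by the investigator will be discontinued from the study". A missed dose alone removes no one; Section 6.3 has it given as soon as possible.

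**After the exit.** Section 7.5 offers one early termination visit: "The assessment and procedures of Visit 4 will be conducted at this visit". Follow-up after discontinuation in Section 5.5.2 covers adverse events only. The early-termination column of Appendix A marks no diary dispensing, no diary collection and no next visit.

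**Primary endpoint.** Section 12.1 compares the diary month before Visit 1 with the month before Visit 4. Section 3.2.1 states: "The monthly mean pain intensity score will be calculated if a participant has at least 80% compliance with the DSD". Section 8.1 puts that at "the equivalent of 23 completed days".

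**Missing data.** Section 12.3 promises an intent-to-treat approach with a binomial mixed model fitted by maximum likelihood under missing at random. It fills missing diary days with the mean of the observed days if fewer than 80% of the month is missing. Above that it carries the previous month forward, for continuous endpoints. If dropout looks informative, it would consider adding baseline covariates.

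**The concern.** The exits most likely to be related to outcome are those caused by a reaction or by inadequate relief, and these are the ones the protocol stops observing. An intent-to-treat analysis then has to assume what these people's last month would have looked like. Missing at random is hard to defend here, because the reason for leaving arises after baseline and nothing commits the model to include it. Yet the primary measure is a home diary entry, so for anyone willing to continue it could be collected. With 20 per arm, a handful of unobserved outcomes is a visible share of the result.

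**Working it through.** **1. Reproduce the 23-day figure.** 80% of a 28-day month (Sections 3.2.1 and 8.1) is 0.80 × 28 = 22.4, rounded up to 23 days. This agrees with Section 8.1.

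**2. Last removal day that loses the score, 23-day rule.** The last cycle starts at Visit 3, Day 56 ± 3 (Section 7.3.3), and ends at Visit 4, Day 84 ± 3 (Section 7.3.4). 56 + 23 = Day 79. Across the Visit 3 window: 53 + 23 = Day 76 to 59 + 23 = Day 82.

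**3. The same under Section 12.3 as written.** Fewer than 80% of days may be missing. 22/28 = 78.6% missing is allowed and 23/28 = 82.1% is not, so 28 − 22 = 6 observed days are enough. 56 + 6 = Day 62. If 20% missing was intended there, at most 5 of 28 days may be missing, 23 days are needed, and the cut-off returns to Day 79. The text does not settle this.

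**4. Share of removals that lose the score.** The documents give no exit timing. Assuming exits spread evenly over Day 0 to 84: 79/84 = 94% under the 23-day rule and 62/84 = 74% under the Section 12.3 wording.

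**5. What the model has instead.** A person removed in the second or third cycle may contribute a Visit 2 or Visit 3 response. A person removed early in the first cycle contributes none: before about Day 0 + 23 = Day 23 on the 23-day rule, or Day 0 + 6 = Day 6 on the looser wording. Missing at random has least support for these people.

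**6. Sensitivity of the result.** Section 12.2 gives 58% and 25% response, 20 per arm and 15% dropout: 0.15 × 40 = 6 people. Assume all 6 lack a score and the stated rates hold in completers, so the completer difference is 0.58 − 0.25 = 0.33. Counting the missing as non-responders:

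| Missing (erenumab/placebo) | Calculation | Difference |
|---|---|---|
| 3/3 | 0.58 × 17/20 − 0.25 × 17/20 | 0.2805 |
| 5/1 | 0.58 × 15/20 − 0.25 × 19/20 | 0.1975 |
| 1/5 | 0.58 × 19/20 − 0.25 × 15/20 | 0.3635 |

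Worst and best case for 3/3: 0.2805 − 3/20 = 0.1305 and 0.2805 + 3/20 = 0.4305, a width of 30 points.

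For scale, the sampling half-width at 20 per arm is 1.96 × √(0.58 × 0.42/20 + 0.25 × 0.75/20) = 1.96 × 0.1468 = 0.288, about 29 points.

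**7. What continued follow-up buys.** If k of the 6 keep a diary, the width is (6 − k)/20: 20, 15 or 10 points for k = 2, 3 or 4.

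**The case against.** Several points on the other side stand.

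- **Day 79 is not the only cut-off.** A reader might infer that every removal before Day 79 leaves no score. Section 12.3 as written scores anyone with 6 diary days in the month, so only removal before about Day 62 fails both rules.
- **The model conditions on more than baseline.** The mixed model in Section 12.3 uses Visit 2 and 3 outcomes, and that section lists rescue medication history and PGIC as possible covariates, if necessary. This helps for later exits due to inadequate relief. It does little for reactions or for exits early in the first cycle, and neither covariate is a commitment.
- **Carry-forward could be read more widely.** The monthly mean is continuous, so it could be carried forward and then classified as response or not. Section 12.3 does not say so. That reading would fill some gaps, but with a value from before the exit.
- **Reaction exits may be few.** Section 6.3 puts constipation and three other reactions below 5% in trials, so about one person in 20 or fewer for constipation. It gives no rate for hypertension or hypersensitivity, and the inadequate-relief route comes on top.
- **The figures in steps 6 and 7 are not estimates of bias.** They compare completers with non-responder counting, and neither is the planned maximum-likelihood analysis. Six is an upper limit, since the 15% is overall dropout and includes withdrawal of consent. In the balanced case the shift is 5 points against a 29-point sampling half-width.
- **The choice of estimand is debatable.** In a 40-person pilot, diary scores after a switch to another drug may credit that drug to either arm.

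A reader might also infer that the diary does continue, because the Visit 4 procedures borrowed by Section 7.5 include diary instructions. Appendix A's early-termination column does not support that, and no later contact is defined at which such a diary would be collected.

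**Conclusion.** The point holds. Six sections make a listed reaction, a decision against the drug, other trigeminal pain treatment, CBT or acupuncture an exit from the study, and diary collection ends there. Removal before about Day 79 fails the endpoint's own 23-day rule; before about Day 62 it also fails the Section 12.3 wording. Unless a carried-forward score is dichotomised, the yes/no primary for these people depends on missing at random given treatment group and any Visit 2 or 3 response.

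A reader might infer that the trial is biased in a known direction. The documents do not support that: reactions would remove more people on erenumab and inadequate relief more on placebo, and neither count is given. What can be said is that each person is 5 points in an arm of 20, and that up to 6 missing scores could matter. The illustration assumes that all 6 lack a score, the arm splits shown, and the planned response rates in completers. The change is worth making because it is cheap and data not collected cannot be recovered later.

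**What to change.** 1. In Sections 2.3.1, 5.5.2, 6.3, 6.6.4, 6.6.5 and 9.3.2, separate stopping injections from leaving the study. Keep every clinical stopping rule, and leave the pregnancy rule in Section 9.4.5 as it is.
2. Unless consent is withdrawn, continue the home diary and the questionnaires to Day 84 and Day 112, by telephone, online or on paper.
3. Amend Section 7.5 and Appendix A (the early-termination column and the diary rows) to match. Do QST, EEG and the blood draw once, at early termination, and do not repeat them at Day 84.
4. Record the date injections stopped and the start of any new trigeminal pain treatment. The reason is already captured on the disposition form (Section 5.5.2).
5. Use these data in the intent-to-treat primary analysis. Add a sensitivity analysis that counts as non-response any withdrawal for a reaction or inadequate relief, and any switch to new trigeminal pain treatment.

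**Cost.** Protocol and consent wording, plus extra diary months and questionnaires for at most about 6 people, with no added clinic procedures. The downside is that some diary data will be off drug or on other treatment, which may dilute the contrast. The recorded dates and the sensitivity analysis let readers judge by how much.

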2.3 Potential Risks and Benefits

2.3.1 Potential Risks

Use of Erenumab: Erenumab is a fully human monoclonal antibody that inhibits CGRP receptor and is FDA approved for the preventive treatment of migraine. As of 16 May 2020, approximately 6,550 people have received erenumab in research studies. Since it was first approved for sale on 17 May 2018, approximately 423,800 people have been prescribed erenumab (Aimovig®) for treatment as of 16 May 2020.

The safety profile of erenumab has been favorable in clinical trials and in the post-marketing setting. A limited number of adverse drug reactions (injection site reactions, constipation, muscle spasm, and pruritus) have been identified at low frequencies (< 5%) in clinical trials. In the long-term use of erenumab, the safety profile remained consistent through 5 years of open-label treatment. In post-marketing settings, hypersensitivity reactions (including rash, angioedema and anaphylactoid reactions) and constipation with serious complications have been reported. In addition, oral sores (eg, stomatitis, mouth ulceration, oral mucosal blistering), alopecia and rash (eg, rash papular, exfoliative rash, rash erythematous, urticaria, blister) have been observed in post-marketing surveillance.

Serious constipation has been reported in patients prescribed erenumab. In some cases, hospitalization or surgery was required. Constipation and the use of medications that decrease gastric motility are in our exclusion criteria, however if a new onset of constipation occurs, the participant will be withdrawn of the study and will be referred to an appropriate practitioner for continued care (see section 9.2).

High blood pressure: High blood pressure or worsening of high blood pressure.

After taking erenumab, antibodies against erenumab may be produced; this has been observed in clinical studies. No side effects associated with these antibodies were observed.

Side effects of the use of erenumab in combination with other drugs are unknown at this time.

There are no adequate data on the developmental risk associated with the use of erenumab in pregnant women or breastfed babies. There are no data on the presence of erenumab in human milk, or on milk production. Pregnant women, breastfeeding women and women planning to become pregnant will be excluded from this study. If a participant

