5.2 Subject Exclusion Criteria

- 1. Participants with a history of congestive heart failure or uncontrolled diabetes.
- 2. Participants with serious hepatic, respiratory, hematologic or immunologic illnesses, an unstable cardiovascular disease, or any other severe acute or chronic medical or psychiatric condition or laboratory abnormality that may increase the risk associated with trial participation or Erenumab or may interfere with the interpretation of trial results and, in the judgment of the investigator, would make the participant inappropriate for entry into this trial.
- 3. Participants with high blood pressure, uncontrolled high blood pressure, malignant disease, chronic constipation, any malabsorption disorders such as IBSc or any other severe acute or chronic medical or psychiatric condition (major depression, schizophrenia, dementia) or laboratory finding that may increase the risk associated with trial participation with Erenumab, that in the judgement of the investigators would interfere with study assessments and/or would make the participant inappropriate for entry into this trial.
- 4. Participants with active malignancy of any type or a history a malignancy (with exception of participants with malignancy surgically removed with no evidence of recurrence within 5 years before enrollment.
- 5. Participants with evidence or a history of drug or alcohol abuse within the past 12 months or has been diagnosed with a substance abuse disorder.
- 6. Participants with dental pain (determined pain of odontogenic/periodontal origin).
- 7. Participants with significant neurological disorders.
- 8. Patients with chronic migraine with and w/o aura following the ICHD-3 criteria treated or not treated with medication
 - Without excluding headache attributed to TMD
- 9. Participants currently taking or have previously taken Erenumab or other CGRP monoclonal antibody (mAmb) or currently taking a CGRP-Receptor antagonist (gepants) for migraine prevention.
- 10. Patients with hypersensitivity to Erenumab
- 11. Participants with trigeminal neuropathic pain taken medications for the management of trigeminal neuropathic pain in where daily dosage has been modified within three weeks before baseline.

- 12. Neuroimaging showing the presence of neurovascular compression or AV malformation.13. Neuroimaging showing the presence of intracranial pathology (i.e. multiple sclerosis, tumor).
- 14. Presence of extracranial pathology in the area of pain (tumor, lesion).

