9.3.2 Expectedness of SAEs

AMGEN and the Study PI will be responsible for determining whether an AE/SAE is expected or unexpected.

The most common adverse reactions (incidence ≥ 3% and more often than placebo) in the migraine studies were injection site reactions and constipation. Common side effects that may affect between 1 and 10 people in every 100:

- Injection site reactions: which may include tenderness, pain, redness, itching, bruising, firmness, or hypersensitivity
- Constipation
- Muscle spasms/cramps

Itching (pruritus)

Since erenumab was approved in May 2018, the following events have been reported in patient's exposed to erenumab in the post-marketing setting:

- 1)Severe allergic reactions such as rash, swelling and difficulty breathing, or swallowing.
- 2) Mouth/lip sores (e.g., stomatitis, mouth ulcerations, and oral mucosal blistering)
- 3) Skin and subcutaneous tissue disorders
- o Alopecia (loss of hair)
- o Rash (e.g., papular rash [small raised red rash], exfoliative rash [redness and/or peeling of skin], erythematous rash [red rash], urticaria [hives], and blisters)
- 4)Constipation and the use of medications that decrease gastric motility are in our exclusion criteria, however if a new onset of constipation occurs, the participant will be withdrawn of the study and will be referred to an appropriate practitioner for continued care (see section 9.2).
- 5) Hypertension or worsening of high blood pressure can happen after receiving Erenumab. Hypertension is in our exclusion criteria, however if a new onset of hypertension occurs, the participant will be withdrawn of the study and will be the participant will be referred to an appropriate practitioner for continued care (see section 9.2)

An adverse event (AE) will be considered unexpected if the nature, severity, or frequency of the event is not consistent with the risk information previously described for the intervention, protocol, investigator's brochure and/or informed consent document.

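### Section 5.2 does not contain the constipation and motility-drug exclusions that 2.3.1, 6.3 and 9.3.2 rely on, so the new-onset constipation trigger misses some people who can be enrolled

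*Combined protocol and SAP*

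**What the plan says.** Section 6.3 gives the premise and the rule together. The premise, with a pointer to the eligibility section, is "Exclusion criteria includes medical history of constipation or taking medications associated with decrease of G.I motility as well as pre-existent hypertension (See 5.2"). The rule is that a participant with a hypersensitivity reaction, or with "new onset constipation or new onset of hypertension", or who no longer wants the drug, leaves the study.

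Section 2.3.1 also says that constipation and motility-lowering drugs are exclusions, and withdraws a participant for new-onset constipation. It reports that some serious constipation cases needed hospital care or surgery. On blood pressure it lists only a risk: "High blood pressure or worsening of high blood pressure". It states neither an exclusion nor a trigger there.

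Section 9.3.2 repeats the exclusion statement for constipation, motility-lowering drugs and hypertension, and the new-onset trigger for both conditions. It also says "Hypertension or worsening of high blood pressure can happen after receiving Erenumab".

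In 5.2, criterion 3 begins "Participants with high blood pressure, uncontrolled high blood pressure, malignant disease, chronic constipation, any malabsorption disorders such as IBSc". It continues with a catch-all for other severe conditions and laboratory findings, and ends with the clause "that in the judgement of the investigators would interfere with study assessments and/or would make the participant inappropriate for entry into this trial". None of the 20 criteria names drugs that reduce gut motility.

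**The concern.** A trigger limited to new onset is complete only if nobody enters with the condition. Sections 2.3.1, 6.3 and 9.3.2 assume that eligibility guarantees this, but staff screen against 5.2, and 5.2 is narrower on constipation and silent on motility-reducing drugs.

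Two things follow. First, a protection that the risk section describes to its readers is not delivered by the criteria actually applied. Second, a participant who enters without constipation and develops it must be discontinued, while one who enters with mild constipation that worsens is left to judgement. The protocol gives no reason for that difference. It appears to arise from the mismatch in wording.

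**Working it through.** No figure in the plan bears on this directly, so the check is a comparison of the text.

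| Section | Constipation excluded? | Motility-reducing drugs excluded? | High blood pressure excluded? | Mandatory trigger |
|---|---|---|---|---|
| 5.2 | Chronic only (criterion 3) | No such criterion | Listed (criterion 3), with an uncontrolled form listed next to it | None (eligibility section) |
| 2.3.1 | Said to be, without limit | Said to be | Not stated; risk only | New-onset constipation |
| 6.3 | Any history, said to be | Said to be | Pre-existing, said to be | New onset of either |
| 9.3.2 | Said to be, without limit | Said to be | Said to be | New onset of either |

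**Who can enter under 5.2 but not under the other three sections**

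1. Current constipation that is not chronic: not listed in 5.2, so admitted unless the investigator uses the general-risk criterion (criterion 20).
2. Constipation in the past, none at Visit 0: admitted under 5.2, but excluded by the wording of 6.3.
3. Users of a motility-reducing drug: admitted under 5.2. Section 6.6.1.1 encourages participants to continue an existing daily pain prescription and sets no condition about gut motility. Criterion 17 removes opioid users, but it is an opioid criterion and does not cover a class defined by effect on the gut.

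**What happens if constipation appears or worsens after an injection**

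- Group 2, and group 3 if free of constipation at entry: a new episode can reasonably be read as new onset, so the mandatory trigger applies.
- Group 1: the condition was already present, so worsening is not new onset. The triggers in 2.3.1, 6.3 and 9.3.2 do not plainly apply.
- What remains for group 1: 9.4.4 makes clinically significant worsening of a condition established at Visit 0 an adverse event. Section 5.5.1 says the investigator may withdraw a participant for an adverse event, for a newly developed exclusion criterion, or at discretion. This route is permissive, whereas 6.3 is obligatory.

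**Size**

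- Injections are given at Visits 1, 2 and 3. After a worsening that follows Visit 1, 3 − 1 = 2 injections remain.
- One participant is 1/40 = 2.5% of the trial.
- The protocol's frequencies are 1 to 10 per 100 (9.3.2) and below 5% (2.3.1 and 6.3). For 20 participants on erenumab these give 20 × 0.01 = 0.2 to 20 × 0.10 = 2 cases, or fewer than 20 × 0.05 = 1 case. They describe constipation as a side effect in general, not worsening in people who already have it, so they indicate scale only.
- The protocol does not say how many of the 200 people to be screened have non-chronic constipation or take such drugs. The number affected cannot be calculated.

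**The case against.** The strongest reply is that worsening is not left uncovered. Section 5.5.1 allows withdrawal for any adverse event that makes staying in the study contrary to the participant's interest. It also allows it when an exclusion criterion develops later, which would catch constipation that becomes chronic. Section 9.1.3 makes severe constipation that may need hospital care a serious adverse event, and 9.5 allows a safety review. This stands. A reader might infer that worsening has no stopping route at all, but the documents do not support that. What is missing is a mandatory trigger specific to the condition.

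The second reply concerns hypertension, and most of it stands. Criterion 3 names high blood pressure outright, and read plainly it agrees with 6.3 and 9.3.2. The uncontrolled form beside it is redundant, and the closing judgement clause reads most naturally with the catch-all before it. A reader might infer that people with controlled hypertension can be enrolled and then fall outside the trigger. That needs a strained reading which 6.3 and 9.3.2 contradict. What remains is an ambiguity about the reach of the clause.

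Third, one might infer that safety counts would not be comparable between participants or arms. The documents do not support this: the trial has one centre, eligibility is settled before randomisation by blinded staff, and safety is analysed descriptively.

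Finally, whether worsening should have its own mandatory rule is a clinical decision. That is correct, and this point does not ask for such a rule. It asks that the stated premise and the eligibility list agree.

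**Conclusion.** The inconsistency is real, and it is firm for constipation and for motility-reducing drugs. Three sections state exclusions that 5.2 does not contain, and the mandatory discontinuation rule is built on them. The gap in the trigger itself is narrow: it concerns people who enter with current, non-chronic constipation that then worsens, and for them withdrawal is discretionary. The motility-drug gap is one of eligibility and exposure, since new constipation in such a person would still meet the trigger. For hypertension, only a clarification of wording is needed.

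The number of participants is unknown and probably small, at 2.5% of the trial each, with up to two injections still scheduled. The point does not depend on that number. It rests on two assumptions: that staff screen from 5.2, and that new onset carries its ordinary meaning. It is worth correcting because the risk concerned is one for which 2.3.1 itself reports serious outcomes.

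**What to change.** Reconcile 2.3.1, 5.2, 6.3 and 9.3.2 as follows:

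- State the constipation exclusion in the same terms in 5.2 and wherever 5.2 is relied on.
- Do the same for motility-reducing drugs: either 5.2 carries the criterion that the other sections cite, or those sections stop citing it.
- Make clear in criterion 3 whether the closing judgement clause applies to high blood pressure, and whether the separate mention of the uncontrolled form is intended.
- Check the new-onset wording of the triggers against whoever the reconciled criteria admit, and make the two consistent.

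Which exclusion and which discontinuation rule apply is for the sponsor's medical team.

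The cost is a protocol text edit and a matching change to the screening checklist. No new data are needed, because medical history, medications, blood pressure and the symptom inventory are already recorded at the study visits. If the broader exclusion wording is the one kept, a few more screen failures are possible among the 200 people expected to be screened.
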